**Table 4: PFS Event and Censoring Method**

Situation	Date of Progression or Censoring	Outcome
No postbaseline disease assessment	Randomization	Censored
Disease progression prior to start of anti-cancer therapy for multiple myeloma	Earliest date that indicates disease progression	PFS event
Death prior to start of anti-cancer therapy for multiple myeloma	Date of death	PFS event
Other, such as: 
 
○ Withdrawal of consent to study participation,
 
○ Lost to follow-up
 
○ Start of subsequent anti-cancer therapy prior to disease progression or death
 
	Date of last disease assessment on or prior to withdrawal of consent to study participation, lost to follow-up, or start of subsequent anti-cancer therapy	Censored

Note, Subjects who were already diagnosed multiple myeloma per baseline central imaging review will be censored at randomization.

### 5.2.2. Estimand

The primary estimand, the main clinical quantity of interest to be estimated in the study, is defined by the following 4 components:

- Population: subjects with high-risk SMM;
- Variable: PFS (see definition above);
- Intercurrent events: 1) start of subsequent anti-myeloma treatment prior to disease progression or death, 2) treatment discontinuation, 3) study discontinuation;
- Population-level summary: Hazard ratio between the two treatment groups.

The strategies to account for the intercurrent events are,

- subjects will be censored at the last disease assessment prior to start of subsequent therapy (while on treatment strategy),
- Treatment discontinuation will be ignored (treatment policy strategy),
- Subjects will be censored at the last disease assessment prior to study discontinuation (hypothetical strategy).

### 5.2.3. Analysis Methods

Analysis of PFS(IRC) will be performed on the ITT analysis set. The Kaplan-Meier method will be used to estimate the distribution of overall PFS for each treatment group. The median PFS with 95% CI will be provided. The Kaplan-Meier curve for PFS will also be plotted by treatment group.

The PFS(IRC) distributions between the 2 treatment groups will be compared using the stratified log-rank test. The p-value from a stratified log-rank test will be reported. The treatment effect (hazard ratio) and its 2-sided 95% CI will be estimated using a stratified Cox regression model with treatment as the sole explanatory variable. The stratification factor used in the analyses will be the number of risk factors associated with progression to multiple myeloma (<3 vs  $\geq 3$ ).

In addition, landmark PFS rate with 95% CI will be estimated by Kaplan-Meier method and reported for each treatment group.

Sensitivity analyses for PFS(IRC) will include PFS(investigator), in which disease progression is determined based on investigator assessment per the IMWG criteria, and PFS(algorithm), in which disease progression is determined based on a validated computer algorithm adapted based on the 2014 IMWG diagnostic criteria for multiple myeloma (Rajkumar 2014). Details of the computerized algorithm is described in a separate document. Both PFS(investigator) and PFS(algorithm) will be analyzed in a similar manner as PFS(IRC).

Supplemental analyses for PFS(IRC) will include,

- 1) subjects who die due to COVID-19 will be censored, i.e. deaths due to COVID prior to start of subsequent anti-cancer therapy for MM will not be counted as PFS events;
- 2) subjects who start subsequent anti-cancer therapy for MM prior to disease progression or death will not be censored;
- 3) If the PFS event date and the latest date of scheduled disease evaluation immediately preceding the event differs more than 2.5 times the disease evaluation intervals (i.e. 30 weeks), which indicates that subject missed at least 2 consecutively scheduled disease evaluation (include hemoglobin, Creatinine, Creatinine clearance, serum FLC assessment, and corrected calcium only), then the event will not be considered as a PFS event in this sensitivity analysis. Instead, the subject will be censored at the date of last disease evaluation prior to the PFS event.

Additional analyses may be performed to assess the impact of COVID-19 as needed.

### **5.3. Secondary Endpoints**

#### **5.3.1. Time to Biochemical or SLiM-CRAB Progression (BOD-PFS)**

##### **5.3.1.1. Definition**

Biochemical or SLiM-CRAB (BOD) progression is assessed based on the validated algorithm according to the definition of biochemical progression per the protocol and the IMWG criteria for diagnostic progression, i.e. either biochemical progression or PFS(algorithm) event. Time to biochemical or SLiM-CRAB (BOD) progression is defined as the time between the date of randomization and the date of first documented evidence of confirmed BOD progression, or death (due to any cause, prior to subsequent MM therapy), whichever occurs first. Subjects who have no postbaseline disease assessment, withdraw consent to study participation, start subsequent anti-cancer therapy prior to BOD progression or death, or who are lost to follow-up, will be censored. In addition, subjects who were already diagnosed multiple myeloma per baseline central imaging review will be censored at randomization.

##### **5.3.1.2. Analysis Methods**

The analysis of BOD-PFS will be similar to the analysis of the primary endpoint PFS described above.

### **5.3.2. Overall Response Rate (ORR)**

#### **5.3.2.1. Definition**

Overall response rate (ORR) is defined as the proportion of subjects with a PR or better response based on the computerized algorithm, per the IMWG response criteria, before the start of subsequent anti-myeloma therapy.

#### **5.3.2.2. Analysis Methods**

The analysis of ORR will be performed on the ITT analysis set. The number and percentage of subjects in the following response categories will be tabulated by treatment group: sCR, CR, VGPR, PR, stable disease (SD), progressive disease (PD), and not evaluable (NE). The overall response (including sCR, CR, VGPR, or PR), VGPR or better (sCR, CR, or VGPR), and CR or better (sCR, or CR) will also be summarized. For each of the above categories, two-sided 95% Clopper-Pearson exact confidence interval (CI) will also be presented by treatment group.

Stratified CMH test will be used to test treatment difference in the proportion of subjects who achieved an overall response. The CMH estimate of odds ratio and its 95% confidence interval and p-value for testing treatment difference will be reported. The analysis will be stratified by number of risk factors associated with progression to multiple myeloma (<3 vs  $\geq 3$ ).

A sensitivity analysis of ORR, in which disease response is based on investigator assessment according to the IMWG response criteria, will be performed in a similar manner as described above.

### **5.3.3. Complete Response Rate**

#### **5.3.3.1. Definition**

Complete response (CR) rate is defined as, the proportion of subjects with a CR or sCR as defined by the IMWG response criteria.

#### **5.3.3.2. Analysis Methods**

The analysis of the response rate of CR or better will be similar to the analysis of ORR described above.

A sensitivity analysis of response rate of CR or better, in which disease response is based on investigator assessment according to the IMWG response criteria, will be performed in a similar manner as described above.

### **5.3.4. Time to first-line treatment for MM**

#### **5.3.4.1. Definition**

Time to first-line treatment for MM is defined as, the time from the date of randomization to the start date of the first-line treatment for MM. Death due to PD without start of first-line treatment for MM will be considered as event. Subjects who withdraw consent to study or are lost to follow-

up or die due to causes other than disease progression or subjects without receiving subsequent anti-cancer therapy will be censored at date of death or the last date known to be alive. Subjects who were already diagnosed multiple myeloma per baseline central imaging review will be censored at randomization.

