2.1.2. Endpoints

Primary Endpoint

The primary endpoint of this study is PFS (defined as the time from the date of randomization to the date of initial documented progression to MM according to the IMWG diagnostic criteria for MM or the date of death, whichever occurs first).

Secondary Endpoints

To demonstrate additional clinical benefit, the following secondary endpoints will be evaluated:

- Time to biochemical or diagnostic (SLiM-CRAB) progression defined as the earlier of time to the earlier of biochemical progression or diagnostic (SLiM-CRAB) progression (see Section 9.2.2)
- Overall response rate (ORR), defined as, the proportion of subjects with a PR or better as defined by the IMWG response criteria
- Complete response (CR) rate, defined as, the proportion of subjects with a CR (or better) as defined by the IMWG response criteria
- Time to first-line treatment for MM, defined as, the time from the date of randomization to the date of the first-line treatment for MM
- Progression-free survival on first-line treatment for MM (PFS2), defined as, the time from the date of randomization to the date of documented progressive disease (PD) on the first-line treatment for MM or death, whichever comes first
- Overall survival (OS), defined as, the time from the date of randomization to the date of death
- Incidence of MM with adverse prognostic features, which include International Staging System Stage III (based on β 2-microglobulin and albumin) and adverse cytogenetic characteristics

- Serum daratumumab PK concentrations and parameters including minimum observed concentration (C_{min}) and maximum observed concentration (C_{max})
- Incidence of anti-daratumumab antibodies and anti-rHuPH20 antibodies
- Change from baseline in global health status and emotional functioning scales of the European Organization for Research and Treatment of Cancer (EORTC) quality of life questionnaire (QLQ)-C30, future perspective scale of the EORTC QLQ-MY20, and utility and visual analog scale of the European Quality of Life Five Dimensions Questionnaire (EQ-5D-5L)
- Duration of response, defined as date of onset of first response until date of disease progression or death
- Time to response, defined as the time from randomization until onset of first response

Exploratory Endpoints

- Identification of novel biomarkers in relation to PFS/OS

Refer to Section 9, Study Evaluations for evaluations related to endpoints.

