11.2. Sample Size Determination

The sample size calculation assumes that the median PFS for Arm A (active monitoring) is 30 months. The longer projected median PFS compared to the published 24 months was chosen to account for the fact that ultra-high risk SMM subjects, who were included in earlier studies, are now considered to have symptomatic MM according to the updated IMWG criteria, and to account for the additional risk factors included to identify high-risk SMM for this study. It was further assumed that daratumumab treatment will reduce the risk of the disease progression or death by 37.5%, ie, assuming a HR (daratumumab vs active monitoring) of 0.625, which translates to a median PFS of 48 months for daratumumab. Taking into account the interim analysis, 165 PFS events are needed to achieve a power of at least 85% to detect this hazard ratio with a log-rank test (one sided alpha=0.025). With a 24-month accrual period and an additional 24 months of follow-up, the sample size needed for the study is approximately 360 (180 in active monitoring, 180 in daratumumab) subjects. Sample size calculations were performed using ADDPLAN v6.1.1.

At the end of study, approximately 134 PFS2 events are expected in both arms (81 at the time of the primary analysis of PFS). With 134 PFS2 events, the probability of showing a positive trend, ie, estimated $HR < 1$, is more than 95% assuming the true $HR = 0.75$ (median PFS2: 72 vs 96 months). Note that in the hierarchical testing procedure, only superiority will be tested for this endpoint.

At the end of study, approximately 107 OS events are expected in both arms (64 at the time of the primary analysis of PFS). With 107 OS events, the probability of showing a positive trend, ie, estimated $HR < 1$, is more than 85% assuming the true $HR = 0.80$ (median OS: 100 vs 125 months).

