11.3.2. Secondary Endpoints

- Time to biochemical or SLiM-CRAB progression (BOD-PFS): The median time to BOD-PFS and 95% CI in each group will be estimated using the Kaplan-Meier method. The BOD-PFS distributions between the 2 groups will be compared using the stratified log-rank test. The treatment effect (HR) and its 2-sided 95% CI will be estimated using a stratified Cox regression model with treatment as the sole explanatory variable.
- ORR: The proportion of subjects who have an OR and the 95% CI will be calculated for each treatment group. The rate of OR will be compared between the 2 groups using the stratified Cochran-Mantel-Haenszel test. The Mantel-Haenszel odds ratio will be provided along with its 2-sided 95% CI.
- CR rate: The proportion of subjects who have a CR or better and the 95% CI will be calculated for each group. The rate of CR or better will be compared between the 2 groups using the stratified Cochran-Mantel-Haenszel test. The Mantel-Haenszel odds ratio will be provided along with its 2-sided 95% CI.
- Time to first-line treatment for MM: The median time to first-line treatment for active MM and 95% CI in each group will be estimated using the Kaplan-Meier method. The time to first-line treatment for MM distributions between the 2 groups will be compared using the stratified log-rank test. The treatment effect (HR) and its 2-sided 95% CI will be estimated using a stratified Cox regression model with treatment as the sole explanatory variable.
- PFS2: The median PFS2 and 95% CI in each group will be estimated using the Kaplan-Meier method. The PFS2 distributions between the 2 groups will be compared using the stratified log-rank test. The treatment effect (HR) and its 2-sided 95% CI will be estimated using a stratified Cox regression model with treatment as the sole explanatory variable.
- OS: The median OS and 95% CI in each group will be estimated using the Kaplan-Meier method. The OS distributions will be compared between the 2 groups using the stratified log-

rank test. The treatment effect (HR) and its 2-sided 95% CI will be estimated using a stratified Cox regression model with treatment as the sole explanatory variable.

- Incidence of MM with adverse prognostic features: The proportion of subjects who progress to MM with adverse prognostic features and the 95% CI will be calculated for each group.

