#### **4.7. Subsequent Anti-myeloma Therapies**

The total number of subjects who received subsequent anti-myeloma therapy for multiple myeloma will be reported for the ITT analysis set in each treatment group. A summary of subsequent anti-myeloma therapy will be presented by therapeutic class, pharmacologic class and preferred term.

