### 5.3.4.2. Analysis Methods

The analysis of the time to first-line treatment of MM will be similar to the analysis of primary endpoint PFS described above.

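### Time to first-line MM treatment: Kaplan-Meier with non-progression deaths censored slightly overstates the proportion reaching treatment and gives too early a median, so a cumulative-incidence estimate should be added

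*SAP*

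**What the plan says.** Protocol 2.1.2 defines the endpoint as "the time from the date of randomization to the date of the first-line treatment for MM" and does not say how deaths are handled.

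SAP 5.3.4.1 splits deaths by cause:
- For deaths from progression: "Death due to PD without start of first-line treatment for MM will be considered as event".
- For other deaths: subjects who "die due to causes other than disease progression or subjects without receiving subsequent anti-cancer therapy will be censored at date of death" or at the last date known alive.

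On the analysis, SAP 5.3.4.2 says: "The analysis of the time to first-line treatment of MM will be similar to the analysis of primary endpoint PFS described above". SAP 5.2.3 therefore supplies the methods: Kaplan-Meier distribution, median and curve, stratified log-rank test and stratified Cox model. It also says that a "landmark PFS rate with 95% CI will be estimated by Kaplan-Meier method and reported for each treatment group". Protocol 11.3.2 is explicit on the median: "The median time to first-line treatment for active MM and 95% CI in each group will be estimated using the Kaplan-Meier method".

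Neither document plans a cumulative-incidence or other competing-risk estimate for this endpoint, or states an estimand for it. The endpoint is not in the testing sequence of SAP 5.1.1 (ORR, PFS2, OS). SAP 4.7 adds a count without a time axis: "The total number of subjects who received subsequent anti-myeloma therapy for multiple myeloma will be reported for the ITT analysis set", by treatment group.

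**The concern.** Censoring assumes that the subject could still have the event later. That is false for someone who has died untreated. With these deaths censored, 1 minus Kaplan-Meier estimates how many subjects would reach treatment if nobody died of other causes. It does not estimate how many of the randomized subjects do.

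The absolute summaries are at stake. A sponsor or clinician will naturally use this endpoint to say how many subjects need MM therapy by a given time, and how long therapy is put off. Those statements come from the curve, the landmark rates and the median. The bias grows with follow-up, and Protocol 17.9.1 plans about 8 years from first randomization.

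**Working it through.** **Design figure first.** Protocol 11.2 states 165 PFS events for at least 85% power at a hazard ratio of 0.625, one-sided alpha 0.025. Schoenfeld's formula gives 4 × (1.960 + 1.036)² / (ln 0.625)² = 163 events, and 165 events give 85.5% power. The ratio of medians also fits: 30 / 0.625 = 48 months. The plan states no figure for time to first-line treatment.

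**Inputs.**
- From Protocol 11.2: median PFS 30 months (Arm A) and 48 months (Arm B); median OS 100 and 125 months; 180 subjects per arm.
- Assumed: constant hazards.
- Assumed: the PFS medians stand in for time to treatment or PD death, because no treatment-start rate is given.
- Assumed: a non-PD death rate before treatment of 0.5%, 1% or 2% per year.

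**Formulas.** Let h = ln 2 / median, so h = 0.02310 (A) and 0.01444 (B) per month. Let d = −ln(1 − annual rate) / 12.
- Kaplan-Meier target: 1 − exp(−ht)
- Cumulative incidence: h/(h+d) × [1 − exp(−(h+d)t)]
- Cumulative-incidence median: −ln[1 − 0.5(h+d)/h] / (h+d)

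**Worked example (Arm A, 1% per year, 36 months).** d = 0.00084. Kaplan-Meier: 1 − exp(−0.832) = 56.5%. Cumulative incidence: 0.965 × [1 − exp(−0.862)] = 55.7%. Median: 30.5 months against 30.0.

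**Results** (gap = Kaplan-Meier minus cumulative incidence, taken before rounding):

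| Arm | Non-PD death per year | Gap at 36 mo (points) | Gap at 60 mo (points) | Median, cumulative incidence vs KM (mo) |
|---|---|---|---|---|
| A | 0.5% | 0.4 | 0.7 | 30.2 vs 30.0 |
| A | 1% | 0.7 | 1.4 | 30.5 vs 30.0 |
| A | 2% | 1.4 | 2.9 | 31.0 vs 30.0 |
| B | 0.5% | 0.3 | 0.6 | 48.6 vs 48.0 |
| B | 1% | 0.6 | 1.2 | 49.3 vs 48.0 |
| B | 2% | 1.1 | 2.4 | 50.7 vs 48.0 |

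At 96 months the gaps are 1.2 to 4.5 points. A simulation at 1% per year (180 per arm, 96 months, 2,000 runs) agrees: at 60 months, 74.9% against 73.5% in Arm A and 58.0% against 56.8% in Arm B.

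**Scale.** Even without censoring, the standard error of the 60-month rate is √(0.75 × 0.25 / 180) = 3.2 points in Arm A and √(0.58 × 0.42 / 180) = 3.7 points in Arm B. Every 60-month gap in the table is below one standard error. At 1% per year, about 4 such deaths per arm are expected by the primary analysis.

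**Sensitivity to the proxy.** If treatment starts more slowly (medians of 36 to 96 months), the 60-month gap at 1% per year is 0.8 to 1.4 points. The median shift grows from 0.7 months (36.7 vs 36) to 5.3 months (101.3 vs 96).

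**Larger death shares.** Suppose the whole planned OS hazard (ln 2/100 and ln 2/125, about 8.0% and 6.4% per year) were untreated non-PD death. The cumulative-incidence medians would be 35.0 and 58.9 months, and the 60-month values 64.2% against 75.0% (A) and 50.5% against 58.0% (B). This is a ceiling, because OS also counts deaths after MM treatment.

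**The comparison between arms.** At 48 months the ratio of log(1 − cumulative incidence) is 0.626 to 0.630, against a cause-specific hazard ratio of 0.625.

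**The case against.** Four points can be made for the plan.

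1. *The comparison is sound.* A stratified log-rank test and Cox model with other deaths censored is a valid cause-specific analysis. This stands. A reader might infer that the hazard ratio is biased; it is not, for that target.
2. *The bias may be trivial.* At 0.5% to 1% per year it is 0.6 to 1.4 points at 60 months. This stands, and it sets the severity. A reader might instead assign half of the planned OS hazard to untreated non-PD death and carve it out of the PFS hazard. That gives 61.0% against 57.0% in Arm A at Month 48 and an Arm B median of 59.4 against 66.8 months. It implies about 4.2% and 3.3% per year, which the documents do not support; their OS medians cover all deaths.
3. *The number treated is already reported.* SAP 4.7 gives a count that Kaplan-Meier does not affect. This stands in part: the count has no time axis and ignores unequal follow-up.
4. *Counting PD death as an event is sensible.* It prevents an untreated MM death from being scored as therapy avoided. This stands. Making every untreated death a competing event would undo that rule.

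A reader might also expect more distortion in the daratumumab arm, because it stays untreated longer. That holds for the median only. The landmark gaps at 36 and 60 months are larger in Arm A.

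**Conclusion.** The point holds for the absolute summaries only. For any non-PD death rate above zero, the planned curve overstates the proportion reaching treatment or PD death, and its median comes too early, in both arms. The amounts rest on constant hazards, the PFS proxy and an assumed death rate that the documents do not give.

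The direction also depends on the target. Against treatment-free survival (treatment or death from any cause), the Kaplan-Meier median is too long: at 1% per year the composite medians are 29.0 and 45.4 months, against 30 and 48. The report must therefore name the quantity it estimates. If a median is not reached, only the curve and landmark rates are affected.

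Severity is low: a small bias in a secondary endpoint with no alpha.

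**What to change.** In SAP 5.3.4.2:
- Add the Aalen-Johansen cumulative incidence per arm, with landmark values and median, taking non-PD death before treatment as a competing event. Use it for absolute statements about subjects treated, and say that the event includes PD death without treatment.
- Keep the event definition of SAP 5.3.4.1. Keep the stratified log-rank test and Cox model, described as cause-specific.
- Keep the protocol-specified Kaplan-Meier median, labelled as hypothetical (no death from other causes).
- Optionally add treatment-free survival as support. It does not depend on the attributed cause of death.

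The cost is one extra analysis and a few lines of SAP text. Date and cause of death are already collected (Protocol 9.1.4). The summary of changes for Amendment 6 says that the primary analysis has concluded and the study has been unblinded. The addition should therefore be presented as supplementary to the Kaplan-Meier results, not as a replacement.

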9.1.4. Follow-Up Phase

The Follow-up Phase will begin once the subject completes 39 cycles or 36 months (whichever occurs first) of active monitoring (Arm A) or daratumumab treatment (Arm B). Reasons for premature discontinuation of active monitoring or daratumumab treatment are listed in Section 10.2. Subjects who discontinue before PD must continue to have disease evaluations as described in Section 9.2, until study completion or confirmed PD (or other reasons as outlined in Section 10). If subjects have not progressed to MM, then no other treatment for SMM or MM is allowed during the study. Follow-up for first-line MM treatment (including the response to first-line MM treatment), second primary malignancies, and survival status will be obtained as specified in the Time and Events Schedule (Table 1). Survival will be followed until the end of the study and at a frequency of at least every 12 weeks until PD. After PD, survival is to be followed at least every 6 months, until the end of the study.

If PRO or survival information is obtained via telephone contact, then written documentation of the communication must be available for review in the source documents. If the subject has died, then the date and cause of death will be collected and documented in the eCRF.

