10.3. Withdrawal from the Study (Arm A and Arm B)

A subject will be withdrawn from the study for any of the following reasons:

- Lost to follow-up
- Withdrawal of consent
- Death
- The study investigator, for any reason, stops the subject's participation in the study
- Sponsor terminates the study

If a subject discontinues active monitoring or study drug and withdraws from the study before the end of the active monitoring or treatment phase, End-of-Active Monitoring or End-of-Treatment Visit assessments should be obtained.

If a subject is lost to follow-up, every reasonable effort must be made by the study-site personnel to contact the subject and determine the reason for discontinuation/withdrawal. The measures taken to follow up must be documented.

When a subject withdraws before completing the study, the reason for withdrawal is to be documented in the eCRF and in the source document. Study drug assigned to the withdrawn subject may not be assigned to another subject. Subjects who withdraw will not be replaced. Additional subjects will not be enrolled. If a subject withdraws from the study, assessments in the End-of-Active Monitoring or the End-of-Treatment Visit should be obtained. If the reason for withdrawal from the study is withdrawal of consent, no additional assessments are allowed. Public record searches will be conducted, if permitted by local law.

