## **5.3.6. Overall Survival**

### **5.3.6.1. Definition**

Overall survival is measured from the date of randomization to the date of death due to any cause. Subjects who are lost to follow-up will be censored at the last known alive date. Subjects who died after consent withdrawal will be considered as having an OS event. Subjects who are still alive at the clinical cut-off date for the analysis or the survival status is unknown will be censored at the last known alive date. The date of last known alive will be determined by the maximum collection/assessment date from among selected data domains within the clinical database.

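### Time to first-line treatment: censoring withdrawn and lost subjects at the last date known alive can count time with unobserved therapy status as therapy-free

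*SAP*

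**What the plan says.** Protocol 2.1.2 defines the endpoint as "the time from the date of randomization to the date of the first-line treatment for MM" and gives no censoring rule. The rule is in SAP 5.3.4.1. One sentence covers subjects who withdraw consent, are lost to follow-up, die of causes other than progression, or receive no subsequent therapy: they "will be censored at date of death or the last date known to be alive". The sentence before it counts a death from progressive disease without first-line treatment as an event.

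Three other places decide what the last date known alive can be:

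- SAP 5.3.6.1 (overall survival): "The date of last known alive will be determined by the maximum collection/assessment date from among selected data domains within the clinical database". The domains are not listed. The same section says "Subjects who died after consent withdrawal will be considered as having an OS event", so vital status found after withdrawal is meant to be used there.
- Protocol 10.3: after withdrawal of consent, "no additional assessments are allowed. Public record searches will be conducted, if permitted by local law".
- Protocol 9.1.4, for subjects still in the study: "Follow-up for first-line MM treatment (including the response to first-line MM treatment), second primary malignancies, and survival status will be obtained". Here therapy and survival are collected together.

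For the primary endpoint, SAP 5.2.1 and Table 4 censor withdrawn and lost subjects at the last disease assessment on or before withdrawal or loss. SAP 5.3.4.2 says that time to first-line treatment is analysed like PFS, and it specifies no sensitivity analysis with an earlier censoring date.

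**The concern.** A last-alive date is the natural censoring date for overall survival, because being alive is the status under study. Here the status under study is whether myeloma therapy has begun. Once a subject has left the study, therapy starts are no longer recorded, yet the rule lets the clock run on to any later alive date or non-progression death date. The subject stays in the risk set while the main event type cannot be observed.

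Take a subject who withdraws at month 10 and is found alive at month 40. The rule counts 40 therapy-free months, and for 30 of them nobody knows whether therapy started.

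Two results are at stake. The Kaplan-Meier therapy-free curve is pushed up in any arm with such subjects. The hazard ratio is distorted if the share of such subjects, or the completeness of tracing, differs by arm. The control arm is open-label and untreated, so unequal withdrawal cannot be ruled out.

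**Working it through.** The documents give no event count, power or effect size for this endpoint, so there is no planned figure to reproduce. The check asks how large the distortion could be under stated assumptions.

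**Assumed inputs (none from the documents).** Exponential time to therapy with medians of 36 months (Arm A) and 56 months (Arm B), so the true hazard ratio is 36/56 = 0.643. Withdrawal is independent of therapy, at a yearly proportion w. A share f of withdrawn subjects is later traced alive at cutoff. There are no deaths. The documents give neither w nor f.

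**Formula, with a common cutoff C = 36 months.** Let λ = ln 2/median, ν = −ln(1−w)/12 and k = λ+ν.

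- Observed therapy-free time per subject: t = (1 − e^(−kC))/k
- Time between withdrawal and cutoff per subject: x = ν(C − t)/k
- The events are the same under both rules, so the apparent hazard is λ·t/(t + f·x).

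**Extreme case: 10% per year in A, 3.5% in B, all traced.**

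- Arm A: λ = 0.01925, ν = 0.00878, t = 22.67, x = 4.175; factor 22.67/26.84 = 0.8445.
- Arm B: λ = 0.01238, ν = 0.00297, t = 27.66, x = 1.614; factor 27.66/29.27 = 0.9449.
- Apparent hazard ratio: 0.643 × 0.9449/0.8445 = 0.719.

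**Modest case: 3% in A, 1% in B, half traced.**

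- Arm A: t = 24.95, x = 1.287; factor 0.9748.
- Arm B: t = 28.65, x = 0.466; factor 0.9919.
- Apparent hazard ratio: 0.643 × 0.9919/0.9748 = 0.654.

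The table sets the formula beside simulations with 400,000 subjects per arm and cutoffs spread over 24 to 48 months. The Arm A median is 36 divided by that arm's factor.

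| Withdrawal per year, A / B | Traced | HR, formula | HR, simulation | Arm A median, formula (months) |
|---|---|---|---|---|
| any | none | 0.643 | 0.64 to 0.65 | 36.0 |
| 3% / 1% | half | 0.654 | 0.65 to 0.66 | 36.9 |
| 10% / 3.5% | half | 0.682 | 0.68 to 0.69 | 39.3 |
| 10% / 3.5% | all | 0.719 | 0.71 to 0.72 | 42.6 |
| 3.5% / 10% | all | 0.579 | 0.57 to 0.59 | 38.2 |
| 10% / 10% | half | 0.645 | 0.64 to 0.65 | 39.3 |
| 10% / 10% | all | 0.646 | 0.64 to 0.65 | 42.6 |

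The medians in the table come from events divided by time. The Kaplan-Meier median, which the SAP would report, moves further: with 10% per year it is about 40 to 41 months with half traced and 45 to 47 with all traced, against a true 36.

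**Second illustration, with the documents' PFS and OS medians as stand-ins** (30 vs 48 and 100 vs 125 months; all deaths censored). The true 36-month therapy-free rates are 0.435 and 0.595.

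- 5% withdrawn by month 24 in both arms, half traced: 0.445 and 0.601.
- 20% in A and 10% in B, all traced: 0.510 and 0.622, hazard ratio about 0.69 against 0.625, Arm A median 37 instead of 30 months.
- Nobody traced: the true rates are recovered to within simulation error.

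The hazard ratios in this second run used 20,000 subjects per arm. With nobody traced they ranged from 0.605 to 0.635, so only its larger shifts mean anything.

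**The case against.** The other side has real points.

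- **The mechanism depends on a date the documents do not guarantee.** The domains behind the last-known-alive date are not listed, record searches depend on local law, and nothing says that they return alive dates rather than only deaths. If nothing is found after the last contact, that contact is the censoring date and there is no bias. This stands: the size cannot be determined from the documents.
- **Most subjects are unaffected.** Under Protocol 10.2, stopping monitoring or treatment does not in itself mean leaving the study, and first-line therapy is still followed. Only full withdrawal or loss matters.
- **The large figures need strong inputs.** Hazard ratios near 0.72 or 0.58 require about a threefold difference in withdrawal together with complete tracing.
- **The endpoint is not tested.** The hierarchy in SAP 5.1.1 is ORR, PFS2 and OS.

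A reader might also infer three stronger things that the documents do not support:

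- *A withdrawn subject can no longer have an event.* SAP 5.3.4.1 counts a death from progression without first-line treatment as an event, and on its face that includes one found after withdrawal. What can no longer be captured is a therapy start.
- *The bias favours one arm.* It goes against daratumumab if Arm A loses more traced subjects and in its favour if Arm B does. The documents do not say which to expect.
- *Arm A subjects leave to obtain treatment elsewhere, and earlier censoring would correct for it.* The documents report no such pattern. If it occurred, withdrawal would be informative, and censoring at withdrawal would be biased as well.

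None of this removes the gap in the rule, which has no cap at the last known therapy status.

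**Conclusion.** The concern holds as a defect in the wording of one secondary endpoint. As written, the rule can count time with unobserved therapy status as therapy-free for withdrawn or lost subjects who have a later alive date or a later non-progression death date.

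Its size is unknown. It is nil if no later vital-status date exists. On the assumed medians of 36 and 56 months, the hazard ratio moves from 0.64 to about 0.65 with 3% vs 1% yearly withdrawal and half traced. It reaches about 0.72, or 0.57 to 0.58 with the arms reversed, with 10% vs 3.5% and all traced. With equal withdrawal the hazard ratio barely changes, but the Arm A median is inflated. These figures assume exponential times, independent withdrawal, no deaths, and traced subjects known alive at cutoff.

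Type I error is not affected, and the primary PFS analysis does not use this rule. The change is still worth making, because it costs little and brings this endpoint into line with the PFS rule.

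**What to change.** Amend SAP 5.3.4.1 so that subjects who withdraw consent or are lost to follow-up, with no first-line therapy recorded, are censored at the last date on or before withdrawal or loss on which subsequent-therapy status was ascertained. Apply this also to those later found to have died. Deaths found only by record search after that date then count neither as events nor as follow-up time in the main analysis.

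Keep the present rule, with traced deaths from progression as events, as a sensitivity analysis. Report by arm how many subjects have different censoring dates under the two rules, and the median gap.

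The cost is one SAP sentence and one extra analysis, with no new data. Protocol Amendment 6 states that the primary analysis has been done and the study unblinded. The amended rule would therefore govern later reporting, and any rerun of the primary-cutoff result should be labelled as specified after unblinding.

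The change removes the unobserved therapy-free time. It does not correct for informative withdrawal.
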